11.2.2	Study Site Staff	22
11.2.3	Data Recording	22
11.2.4	Investigator Documentation	22
11.2.5	GCP Training	22
11.2.6	Confidentiality	22
11.2.7	Data Protection	22
12	STUDY CONDUCT RESPONSIBILITIES	22
12.1	PROTOCOL AMENDMENTS	22
12.2	MANAGEMENT OF PROTOCOL NON COMPLIANCE	23
12.3	SERIOUS BREACH REQUIREMENTS	23
12.4	STUDY RECORD RETENTION	23
12.5	END OF STUDY	23
12.6	CONTINUATION OF TREATMENT FOLLOWING THE END OF STUDY	23
12.7	INSURANCE AND INDEMNITY	24
13	REPORTING, PUBLICATIONS AND NOTIFICATION OF RESULTS	24
13.1	AUTHORSHIP POLICY	24
13.2	DISSEMINATION OF RESULTS	24
14	REFERENCES	24

LIST OF ABBREVIATIONS

ACCORD	Academic and Clinical Central Office for Research & Development - Joint office for The University of Edinburgh and Lothian Health Board
AE	Adverse Event
AR	Adverse Reaction
CI	Chief Investigator
CRF	Case Report Form
EPCC	Edinburgh Parallel Computing Centre
GP	General Practitioner
GCP	Good Clinical Practice
ICH	International Conference on Harmonisation
ICF	Informed Consent Form
MHRA	Medicines and Healthcare products Regulatory Agency
NHS	National Health Service
PI	Principal Investigator
PIL	Participant Information Leaflet
QA	Quality Assurance
REC	Research Ethics Committee
RDU	Rheumatic Diseases Unit
SAE	Serious Adverse Event
SAR	Serious Adverse Reaction
SHARE	Scottish Health Research Registry
SOP	Standard Operating Procedure
SUSAR	Suspected Unexpected Serious Adverse Reaction
WGH	Western General Hospital

Study title:	
Type of study	Feasibility study
Trial participants	Patients with diagnosis of gout requiring urate lowering therapy
Planned sample size	60 participants and 60 non-gout controls
Follow-up duration	1 year for GoutSMART study, further 2 years if participating in GoutSMARTER extension
Planned trial period	2 years (4 years in total with GoutSMARTER extension)
Primary objective	Assessment of supported self-management of gout
Secondary objectives	Measurement of gout flare frequency and health related quality of life Evaluation of cost effectiveness and safety of the approach Assessment of treatment adherence Identification of uric acid load in faecal samples and correlation with gut microbiome characteristics. Assessment of compliance with dietary modification and impact on serum urate levels.
Primary endpoint	Proportion of participants achieving urate levels of $\leq 0.3\text{mmol/L}$ at 24 weeks
Secondary endpoints	Proportion of participants achieving urate levels of $\leq 0.3\text{mmol/L}$ at 52wks (and for extension 104wks and 156wks) Medication compliance assessed by patient self-report and serum oxypurinol Number of days of self-reported gout flare Size in mm of the largest tophus (index tophus) and number of clinically evident tophi Self-reported quality of life during/following gout flare evaluated using the EQ-5D-5L questionnaire Number of days lost at work and number of scheduled and unscheduled medical appointments or hospital admissions due to gout Proportion of patients achieving a dose reduction of urate lowering therapy in the extension phase Proportion of patients achieving sustained dietary modifications and relative reduction of urate lowering therapy in the extension phase.
Device name	BeneCheck plus
Manufacturer name	General Life Biotechnology Co Ltd, Taiwan
Principle intended use	Self-management of gout by patients in the community managed by the general practitioner

1 INTRODUCTION

1.1 BACKGROUND AND RATIONAL

Gout is the most common cause of inflammatory arthritis with prevalence in the UK estimated at 2.5%, and an incidence that is rising globally alongside epidemics of obesity and cardiovascular disease. For patients it is characterised by sudden attacks of pain of great intensity, and is a cause of reduced quality of life, work absence and disability. For health services gout is an increasing cause of emergency attendance, hospital admission, and prolonged hospital stays. Recent guidelines have emphasised the importance of maintaining urate below target levels in order to achieve long term prevention of gout attacks (Khanna J, 2012). Within clinical trials or with sufficient support it is clear that the vast majority of patients are able to achieve target serum urate levels, though in routine clinical practice patients rarely meet current recommendations. High levels of serum urate can result in the formation of urate crystal deposits under the skin (called tophi) which are a marker of severe disease. These will resolve if serum urate levels are held low for a sustained period of time. Tight control of gout with a target of urate at or below 0.3mmol/l should achieve disease remission (clearance of all crystals from the body), but once this has been achieved recent guidelines suggest that keeping urate levels at or below 0.36mmol/l should prevent recurrence of disease. There is no consensus on how long tight control of urate is required, nor is there published experience of long term disease related outcomes in gout patients that have achieved target urate levels.

A new paradigm of care for patients is required. Providing patients with the means to measure their own levels of serum urate would reduce the requirement for review appointments needed to guide escalation of therapy to achieve target, and possibly reinforce patient adherence to treatment. Suitable monitoring devices for urate self-testing are already available and have been reported to show excellent reliability in comparison to gold standard laboratory diagnostics (Paraskos J, 2016). Within our unit there is already experience in the use of applications for smart phones facilitating patient feedback of self-testing results, and the interactive nature of this approach provides additional opportunity for providing support to patients at time of need. This could help establish a patient led approach to gout management, similar to the 'treat to target' approach adopted in the management of diabetes.

We also aim to understand the contribution of the gut microbiome to the pathogenesis of gout. Little is known about the factors that contribute to uric acid and purine availability within the gut lumen. Some preliminary evidence (Guo Z, et al. 2016) has suggested that gut bacteria resident in patients with gout is different than controls. We would like to challenge and develop this hypothesis by quantifying the availability of purine and urate metabolites within the gut as well as the metabolic potential of gut microbes known to play a role in uric acid and purine metabolism. This section of the study may pave the way for future development of anti-microbial, dietary modification or probiotic agents that may contribute to reducing uric acid availability within the gut and the burden of gout in the wider population.

It has long been suggested that certain lifestyle factors including dietary factors impact the risk of hyperuricaemia and gout. The British Society for Rheumatology Guidelines for Management of Gout (Hui M, et al. 2017) includes that all patients with gout should be encouraged to follow a well-balance diet low in fat and added sugars, high in vegetables and fibres specifically advising the avoidance of sugar-sweetened soft drinks containing fructose, high-purine foods and reducing alcohol intake. However, implementing this knowledge and routinely including this step in the management of patients with gout is challenging due to a variety of factors including limited time resources in primary care. The GoutSMART application provides the opportunity to educate patients of beneficial lifestyle modifications and encourage implementation with direct feedback through control of urate levels and regular review by the healthcare professional. Lifestyle changes may ultimately allow the use of lower doses of urate lowering therapy. During an extension phase, we aim to offer individualised dietary advice based on a Food Frequency Questionnaire for those patients with elevated consumption of certain foods, and then review dietary compliance and its impact on urate levels via frequent urate level testing and repeat Food Frequency Questionnaires during a block of intervention.

2 STUDY OBJECTIVES

2.1 Objectives

2.1.1 Primary Objective

- To assess supported self-management of gout using an application on a smart phone and self-testing of serum urate.

2.1.2 Secondary Objectives

- To measure gout flare frequency and health related quality of life.
- To assess treatment adherence measuring oxypurinol, the active metabolite of Allopurinol
- To evaluate the cost-effectiveness and safety of the approach by gathering data including hospital and GP visits and work absenteeism, and adverse events.
- Identification of uric acid load in faecal samples and correlation with gut microbiome characteristics.
- To assess feasibility of implementation, compliance and impact of dietary modification on serum urate levels.

2.2 ENDPOINTS

2.2.1 Primary Endpoint

- Proportion of participants achieving urate level $\leq 0.30\text{mmol/L}$ at 24 weeks.

2.2.2 Secondary Endpoints (assessed at week 24 and 52, and for extension study also at week 104 and 156)

- Proportion of participants achieving urate level $\leq 0.3\text{mmol/l}$ and $\leq 0.36\text{mmol/l}$
- Prospectively gathered number of days of self-reported gout flare over course of study
- Size in mm of the largest tophus at baseline (index tophus)
- The number of clinically evident tophi
- Prospectively gathered self-reported quality of life during/following gout flare evaluated using the EQ-5D-5L questionnaire over course of study
- Prospectively gathered data on days lost at work due to gout flare over course of study
- Prospectively gathered number of scheduled and unscheduled medical appointments/ hospital admissions due to gout over course of study
- Self report of number of doses of medication omitted in preceding 2 weeks will be collected at all study visits
- Plasma oxypurinol levels will be measured at study visits where possible
- Proportion of patients achieving a dose reduction of urate lowering therapy in the extension phase whilst maintaining target urate levels.
- Proportion of patients achieving sustained dietary modifications with reduction of urate levels, and/or further reduction of urate lowering therapy dose in the extension phase.

3 STUDY DESIGN

3.1 Original study

[figure not shown]
This is a feasibility study. A total of approximately 60 patients will be recruited from rheumatology clinics or rheumatology on-call services in NHS Lothian. Participants will be randomized to the intervention group in a 2:1 ratio. Based on baseline renal function and serum urate levels, and in line with local protocol, an individual treatment plan will be drawn up for all participants with the goal to achieve serum urate level of $\leq 0.30\text{mm/L}$. A sample from a 24 hour urine collection and paired serum creatinine and urate sample from each participant will be analysed for urate metabolites. The treatment plan will be communicated to the patient and their general physician.

All participants will have a smart phone application developed by IT specialists in the EPCC uploaded to their smart phones. Control participants will have a limited version of the GoutSMART application installed with background information about gout and providing a means for participants to enter details of gout flare frequency and quality of life through the trial. Subjects in the intervention group will be taught to self-test serum urate using a BeneCheck Plus hand held device and provided with test strips. A full version of the GoutSMART application will be installed with the features mentioned above but also incorporating advice on urate monitoring and medication titration. Participants will be prompted to check their serum urate on two separate days and enter the results into the GoutSMART application. The application will respond by a) a suggestion to increase urate lowering therapy or b) to stay on the current dose of allopurinol. If the patient needs to increase allopurinol there will be an automatic reminder two weeks after any increased dose of urate lowering therapy prompting the patients to test their own urate levels on two separate days and submit updated readings which will be handled in the same way as described above. Conversely for participants achieving target levels this will be acknowledged and a request to resubmit readings will be sent on a monthly basis until 3 consecutive target readings have been obtained. 6 months is given until review reflecting current practice.

The main outcome will be urate levels at week 24, with a secondary outcome being urate levels at week 52. Where participants are able to attend hospital then both serum and capillary urate will be obtained and the serum urate will be used as the study outcome, however we anticipate that a capillary urate only will be obtained in participants required to self-isolate or maintain social distancing during the coronavirus pandemic and this will be used to determine the urate level at week 24 and 52 for affected participants. To assess treatment compliance drug metabolite levels will be tested from serum samples obtained at week 24 and 52 visits where possible, and by self report in all participants. All patients will be assessed for tophi at baseline by clinical exam, and again at week 24 and 52. This will be by examination if participants are able to attend hospital, or by review of submitted images where attendance at hospital is not appropriate due to coronavirus restrictions. All participants will be asked once per month to record flares, measurements of quality of life, number of hospital and GP visits as well as days off work via the application. The study is designed for a total (post-randomization) duration of 52 weeks. Subjects who withdraw or disengage before the 24 week visit will not be considered to have completed the study.

For the gut microbial aspect of this study, eligible participants will fill in an online semi-quantitative food frequency questionnaire (FFQ, Scottish Collaborative Group – see Zgaga et al, PLOSone 2012). Patients will also provide an early morning urine sample for urinary metabolomic analysis and a fresh faecal sample for subsequent faecal metabolomics and shotgun metagenomics. To provide suitable controls, patients will be asked whether they are happy that a family member be contacted to provide control samples for this analysis. In this case, first or secondary sex-matched controls without gout will be contacted by the study team for a once-off visit (Medical history, bloods – serum urate LFTs, renal function, FFQ and urine and stool samples). Patients can opt out of having a family member involved if they wish in which case local controls (age-similar and sex matched) will be recruited from the staff of the University of Edinburgh.

Figure 1: Study Design

3.2 Extension phase

Urate-lowering therapy requires a long term commitment from the patient and health care provider. We know that levels of medication adherence in gout are unusually low (Dehlin M, 2017 and Briesacher BA, 2008). A recent randomised controlled trial comparing specially trained nurses leading care versus usual care in the UK, showed that with dedicated surveillance and monitoring, the use of urate lowering therapy is significantly higher at 1 and 2 years in the nurse-led compared to the usual care group (Doherty M, 2018). The GoutSMART approach may provide an alternative means for patients to monitor their disease and increase awareness of the role and importance of long-term urate lowering therapy for disease control thereby increasing adherence. At the 12 month study visit all participants will be invited to participate in a 2 year extension to the study which will evaluate long term compliance with medication along with clinical outcomes. Additional participants will be invited to take part in

this long term monitoring arm of the study and will be randomised 1:1 to active monitoring or routine care. All participants taking part in this extension study will have their medication optimised using the GoutSMART approach to ensure that their urate level is at target of 0.3mmol/l or less.

For participants in the active care arm of the study ongoing monitoring of self-reported urate will be performed until participants meet criteria for disease remission. For the purposes of this study we will define disease remission to have been achieved if all three of the following outcomes have been achieved:

[figure not shown]
- 1) Resolution of clinically evident tophi
- 2) Urate levels at or below 0.3mmol/l over preceding 12 months (with minimum of 3 separate readings obtained in different months).
- 3) Resolution of gout flares (self-reported) for 12 months

When remission has been achieved by these criteria then participants will be given the option to reduce their dose of allopurinol in line with current best practise guidelines which suggest that maintaining urate below 0.36 mmol/l is sufficient to maintain remission, and that long term urate levels should not be held below 0.18mmol/l.

Participants that were assigned to usual care will have their care optimised using the GoutSMART approach until they have achieved a urate at or below the target of 0.3mmol/l, but in line with usual clinical practise will have no further titration of their medication or outpatient clinical review after this point. Outcomes will be reviewed at 12 months, 24 months, and 36 months as part of the extension study.

In addition, all patients in the active care arm will be invited to participate in a dietary modification substudy during the extension phase. Those in whom aspects of dietary discordance with current BSR guidelines have been identified utilising the Food Frequency Questionnaire, will be offered an individualised plan of dietary modifications to be implemented over a period of time lasting up to three months. Regular measurements of urate levels and diet feedback will monitor progress.

Figure 2: Study Design Extension Phase

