4 STUDY POPULATION

4.1 NUMBER OF PARTICIPANTS

We aim to recruit approximately 60 participants. Recruitment will remain open until sufficient numbers of recruited participants has been reached. Additional participants satisfying the same inclusion and exclusion criteria (but without any urate threshold requirement) will be recruited into the extension study to ensure sufficient power is maintained). An equal number of control participants will be recruited for the purposes of the gut microbiota analysis.

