6.1.4 Follow-up visit week 52 (and for extension study week 104 and 156)

Participants will be invited to the RDU clinic for review of secondary outcomes, or alternatively if hospital attendance is not appropriate due to recommendations to self-isolate or maintain social distancing due to the coronavirus pandemic then this assessment will be made by telephone. The patient diaries generated by the GoutSMART application will be reviewed and any adverse advents recorded. All participants will be asked to record the number of doses of medication missed in the preceding 2 weeks. A physical examination will be performed to assess the size and number of tophi or submitted images will be reviewed. Finger prick and/or serum urate will be measured along with blood tests of renal and liver function tests and oxypurinol levels.

All participants completing the study at week 52 will be offered participation of the extension phase of the study. Written information will have been provided prior to their week 52 review about the extension. Consent will be gained from those choosing to participate in the extension phase. A treatment plan will be formulated for all participants. Participants of the intervention arm in remission will be offered to reduce the dose of their urate lowering medication and self-reassess every two weeks (update urate levels, entering disease activity

data) until remission maintenance is achieved. Feedback will be provided in the usual GoutSMART application manner. Participants of the control arm will continue as per routine care. Once remission maintenance is achieved monthly urate reading will be requested. The participant will be asked to enter additional urate readings and QoL information during flares.

For those opting into the dietary lifestyle intervention arm, a personal management plan with dietary adjustments where appropriate will be formulated based on the Food Frequency Questionnaire which each participant will fill in at baseline. Participants will be asked to perform weekly urate measurements, weight measurements and report on flares via the app. Feedback will be provided by the research team at least weekly for the first 4 weeks, then monthly for three months. Participants will be asked to fill in the Food Frequency Questionnaire at extension baseline, monthly for three months and at the end of study.

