8 STATISTICS AND DATA ANALYSIS

8.1 SAMPLE SIZE CALCULATION

This is a feasibility study which is intended to establish whether the proposed self-management approach can be realised in practice, and if so to inform the design of a larger study that would look to establish the cost-effectiveness of this approach.

The numbers chosen are based on previous audits in primary care performed which revealed that only 24% of gout patients reached a target of 0.30mmol/l of serum urate when receiving standard care by GPs who were given an algorithm for management of gout beforehand. We have assumed that about 25% of patients assigned to routine care will achieve the target of 0.3mmol/l in the control group. We are anticipating that we will achieve target levels of urate in 75% of patients in the intervention group which though ambitious is still well below the 92% achieved in a recent UK study (Rees, F. 2013). Based on these estimates a sample size of n=34 in the intervention group and n=17 in the control group (2:1 randomisation) provides 82% power to detect an effect of 25% in the control group and 75% in the intervention group (assuming a two-sided 5% significance level), after taking into account a 15% drop-out rate.

For the extension study we have assumed that 90% of participants in the Smart care arm of the study remain adherent to therapy, compared with only 50% in the usual care arm. These figures are conservative compared to 95% compliance reported in Doherty et al (2018) and 36.8% medicine possession ratio reported in Briesacher et al (2008). A sample size of 20 in each allocation yields 81% power, and 30 in each treatment allocation 94% power to detect such a difference. Due to observed drop outs from the feasibility study and restrictions in recruiting participants during the COVID pandemic we will recruit additional participants into the extension phase of the study to ensure sufficient power is achieved.

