8.2 PROPOSED ANALYSES

The primary outcomes of the study will be the proportion of participants achieving urate level $\leq 0.3\text{mmol/l}$ at 24 weeks in participants receiving supported self-management compared to those receiving usual care. Comparison of proportions will be performed using the Chi-square test of independence, or Fishers Exact test for where expected values in any cell of the contingency table are less than 5, with results displayed as frequency (percentages). The proportion of participants achieving serum urate level $\leq 0.3\text{mmol/l}$ at all subsequent assessments will be analysed in the same fashion. Patients with undetectable levels of oxypurinol will be deemed to be non-compliant and a similar analysis will compare the proportion of participants in each treatment allocation that are non-compliant. For these analyses an intention to treat analysis will be performed with participants that have dropped out of the study being included as failing to reach target, or non-compliant with medication respectively.

Continuous outcome measures include the size in mm of the largest tophus at baseline (index tophus) measured at 52 weeks, and the number of clinically evident tophi evaluated at 52 weeks. Further continuous outcomes include the number of days lost at work due to gout flare, number of scheduled and unscheduled medical appointments/ hospital admissions, self report of number of doses of medication omitted in 2 weeks prior to study visits at week 24 and 52. Two-tailed independent student t-tests will be applied for between group comparisons of normally distributed data. Results will be displayed as mean \pm standard deviation (SD). A Mann Whitney U test (MWU) will be applied when the variables are not normally distributed, with results given as median (interquartile range IQR). Although a nominal value of significance of $p<0.05$ for these exploratory measures will be adopted, given the number of secondary outcomes listed a Bonferroni correction will be applied and reported alongside each result.

Although health reported quality of life data will be gathered this is exploratory data that will not be analysed directly but be used to inform the design of a larger health economic study.

Statistical analysis will be performed using Minitab version 16 (Minitab Inc., Pennsylvania, US) or the Statistical Package for Social Services version 19 (SPSS IBM Corp, NY State, US).

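### Extension comparisons should be stratified by cohort, because completers were randomised 2:1 and new recruits are randomised 1:1

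*Combined protocol and SAP*

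**What the plan says.** - **Completers.** Section 3.1: "Participants will be randomized to the intervention group in a 2:1 ratio". Sections 3.2 and 5.1 invite week-52 completers from both arms into the extension. No re-randomisation is described, and the text reads as though each person keeps the original arm: "Participants that were assigned to usual care will have their care optimised using the GoutSMART approach" (3.2, until target is reached) and "Participants of the control arm will continue as per routine care" (6.1.4).
- **New recruits.** Section 3.2 brings additional participants into "this long term monitoring arm of the study and will be randomised 1:1 to active monitoring or routine care". Section 4.1 sets their entry rules: "Additional participants satisfying the same inclusion and exclusion criteria (but without any urate threshold requirement) will be recruited into the extension study". The original cohort needed a serum urate above 0.36 (4.2).
- **Purpose of the new recruits.** Section 8.1: "we will recruit additional participants into the extension phase of the study to ensure sufficient power is achieved".
- **Analysis.** Section 8.2 compares proportions by arm with a chi-square test, or Fisher's exact test when an expected count is below 5. The proportion reaching 0.3 mmol/l "at all subsequent assessments will be analysed in the same fashion". Non-compliance, judged by undetectable oxypurinol, gets a similar comparison by allocation. Both use an intention-to-treat rule with "participants that have dropped out of the study being included as failing to reach target, or non-compliant with medication respectively".

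Cohort is not named as a stratum, a covariate or a sensitivity analysis.

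**The concern.** Recruiting people only to reach a power target makes sense if they are analysed together with the completers. Pooling a 2:1 cohort with a 1:1 cohort puts a larger share of completers in the active arm than in the control arm.

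The cohorts may also differ in outcome. Completers are a retained group with a year in the study behind them. New recruits have had no such year and face no urate threshold. If outcomes do differ, the crude arm difference contains part of the cohort difference. It favours the active arm if completers do better and the control arm if they do worse.

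The estimates are meant to inform a larger trial (8.1, 13.2), so a shifted estimate matters even when the significance test is little affected.

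A related gap is that 8.2 does not say whether its dropout rule covers original participants lost before week 52. The denominator of the extension comparison is therefore unclear.

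**Working it through.** **The plan's own figure.** Section 8.1 states 81% power with 20 per arm and 94% with 30 per arm for 90% versus 50% adherence. The pooled-variance normal approximation (two-sided 5%, equal arms, no continuity correction) gives 81.3% and 94.3%, so both figures reproduce.

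**Inputs.** The ratios (2:1 and 1:1), the planned effect (90% versus 50%) and the test come from the protocol. The two-sided 5% level is stated for the original study and assumed for the extension. Cohort sizes and cohort rates are assumptions. With 20:10 completers (active:control), at least 20 per arm needs 10:10 new recruits and at least 30 per arm needs 20:20.

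**Share of a cohort gap that passes through.** For completers a:b and new recruits c:d:

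pass-through = a/(a+c) − b/(b+d)

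- 20:10 + 10:10: 20/30 − 10/20 = 16.7%
- 20:10 + 20:20: 20/40 − 10/30 = 16.7%
- 34:17 + 3:3: 34/37 − 17/20 = 6.9%

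For completers 2m:m and new recruits r:r, put t = r/m. The pass-through is then 1/(t + 3 + 2/t). It is largest at t = √2, where it equals 3 − 2√2 = 17.2%.

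**Bias = pass-through × cohort gap.** At 16.7%, gaps of 10, 30 and 40 points give 1.7, 5.0 and 6.7 points. As a check, take no arm effect, completers at 90%, new recruits at 60%, and 20:10 + 10:10. The active arm is (20×0.9 + 10×0.6)/30 = 80% and the control arm is (10×0.9 + 10×0.6)/20 = 75%, a spurious 5 points.

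**Rejection rate of the 8.2 test when the arms do not differ** (exact enumeration):

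| Layout | Completer / new-recruit rate | Total | Favouring active | Favouring control |
|---|---|---|---|---|
| 20:10 + 10:10 | 70% / 70% | 4.4% | 2.3% | 2.2% |
| 20:10 + 10:10 | 80% / 70% | 4.1% | 2.8% | 1.3% |
| 20:10 + 10:10 | 90% / 60% | 4.4% | 4.0% | 0.4% |
| 20:10 + 20:20 | 70% / 70% | 5.1% | 2.5% | 2.6% |
| 20:10 + 20:20 | 80% / 70% | 5.3% | 3.6% | 1.7% |
| 20:10 + 20:20 | 90% / 60% | 6.3% | 5.8% | 0.6% |

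**Stratified by cohort.** The Cochran-Mantel-Haenszel test at 90% / 60% (200,000 simulations) rejects in 4.6% of trials with 10:10 (2.4% active, 2.2% control) and 5.3% with 20:20 (2.8%, 2.5%). The errors are roughly balanced again.

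**Sensitivity to attrition.** If drop-out left completers at 20:5 with 15:15 new recruits, the pass-through would be 20/35 − 5/20 = 32%. The bias at a 30-point gap would be 9.6 points and the type I error 11.2%, against 4.8% stratified. The protocol gives no attrition by arm, so this shows only that the 17.2% ceiling depends on the 2:1 ratio surviving.

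**The case against.** The strongest objection is size. The harm depends on a cohort gap that the protocol does not give, and parts of the text suggest a small one. Section 3.2 optimises everyone to target, and new recruits meet the same criteria apart from the urate threshold. At a 10-point gap the bias is 1.7 points against a planned 40. With 10:10 recruits the two-sided error rate is 4.4% whether the gap is 0 or 30 points. The 20:5 layout has no source and should carry no weight in grading the point. All of this stands. However, optimising urate at entry does not equalise later adherence, on which the extension is powered, and an unchanged two-sided rate hides the shift of errors to one side.

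Second, pooling and retained allocation are inferred. Figure 2, the extension design, could not be read for this review and may show how the cohorts enter the arms. That lowers certainty, but sections 3.2, 6.1.4 and 8.1 all point the same way.

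Third, the 8.2 sentence on subsequent assessments concerns the urate target. For non-compliance the plan promises only a similar analysis and names no time points. That is correct, but neither outcome has a stratified analysis.

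Fourth, an intention-to-treat rule does exist. It is ambiguous only for people lost before the extension began.

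**Conclusion.** The concern holds. If the cohorts are pooled and completers keep their arm, the crude extension comparison is confounded by cohort whenever outcomes differ between cohorts. With exact 2:1 and 1:1 ratios at most 17.2% of the cohort gap passes through: under 2 points for a 10-point gap and about 5 for a 30-point gap. The direction depends on which cohort does better. This does not invalidate the extension, and a true 40-point effect would remain plain. It should be corrected because the bias is avoidable and the estimates will feed a larger trial. Confidence is medium, since the cohort sizes, the cohort rates and the two structural conditions are not stated.

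**What to change.** In section 8.2:

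1. State whether completers and new recruits are pooled, and whether completers keep their original allocation.
2. Define the extension analysis set, including whether original participants lost before week 52 count as failures or as non-compliant.
3. Stratify every between-arm extension comparison of proportions by cohort, using Cochran-Mantel-Haenszel (exact version if sparse) with a stratified risk difference, and show results by cohort.
4. Note that this removes confounding by cohort only. The completer stratum remains open to selection after randomisation.

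Separately, reconcile the extension criterion in 4.2, which requires completion of week 52, with 3.2, 4.1 and 8.1, which recruit people who have not been in the original study.

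The cost is a few sentences, since cohort is known for everyone. Power at 90% versus 50% is 89.3% stratified against 87.9% unstratified (20:10 + 10:10), and 96.9% against 97.3% (20:10 + 20:20). The exact stratified test gives about 85% and 95.4%, a loss of 2 to 3 points against the unstratified test.
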